5.3.2.1.2. Statistical methodology for time to event data

The analysis of time-to-event data are conducted using Kaplan-Meier (KM) estimates of events over time. Estimates of the event rate are obtained for each study treatment group using the KM method as implemented in SAS proc lifetest. The reference time is the study day, i.e., days elapsed since first treatment. The KM estimates at different time points are plotted together with the 95% two-sided confidence limits (CLs), calculated using Greenwood's formula for the estimate of the standard error. Intervals will be displayed by 24 weeks up to last available time point.

The SAS code for the KM analysis is as follows:

```
proc lifetest data= method=KM;
time survtime*censor(1);
run;
```

CONFIDENTIAL – FOIA Exemptions Apply in U.S.

5.3.2.2. Analysis of relapse-related variables

5.3.2.2.1. Main analysis of ARR

The main statistical analysis will be performed on the FAS and EXTS using all data in the Combined Analysis Period. The model described in Section 5.3.2.1 for confirmed relapses will be used, with core study treatment as a factor and the logarithm of time in study (in years) from randomization up to the end of the Combined Analysis Period as an offset variable. ARR will be summarized descriptively by core treatment group in a table for confirmed relapses as follows:

- Number of confirmed relapses per subject: descriptive statistics;
- Number of confirmed relapses per subject: frequency counts and percentages for categories 0, 1, 2, 3, 4, 5-10 and 11+;
- Total number of confirmed relapses: frequency count:
- Total time in study (subject years): sum;
- Raw ARR: total number of confirmed relapses / total time in study.

Mean model-based estimates of the ARR (for confirmed relapses), by core study treatment group, as well as 95% CIs will be presented. A rate ratio comparing ponesimod with teriflunomide 14 mg will be derived from the model including 95% CIs.

The fit of the model will be assessed and other distributions such as the Poisson distribution will be considered in case of a lack of fit.

5.3.2.2.2. Additional analyses of ARR

All relapses will be analyzed for the Combined Analysis Period on the FAS and EXTS as described in Section 5.3.2.1.1, i.e., including the first summary table described (and adding the ARR estimate and 95% CI from a NB model).

This approach will also be used to analyze confirmed relapses on:the Extension Analysis Period using the EXTS and the EXTS and for all relapses on:

• the Extension Analysis Period using the EXTS;

with the logarithm of the appropriate observation time during the related period as an offset variable.

Additionally, for confirmed relapses, the ARR estimate and 95% CI from a Poisson model (as the NB model is not expected to converge for all time periods) will be determined by 24-week period (as defined in Section 5.3.1) using FAS and EXTS as follows. The log of observational time during each interval will be used as offset.

- Core Analysis Period (core weeks 0-24, 24-48, 48-72, 72-96, 96-core EOS);
- Extension Analysis Period (extension weeks 0-24, 24-48, 48-72, 72-96, 96-120, 120-144, 144-168, 168-192, 192-216, 216-Extension EOS).

A line plot will be created to present the ARR estimate and the corresponding 95% CI by 24 weeks period.

Relapse characteristics will be summarized using descriptive statistics for the Combined Analysis Period on the FAS and for the Extension Analysis Period on the EXTS. This includes the following:

- Number (%) of subjects with at least one: relapse, relapse requiring hospitalization, relapse treated with corticosteroids; for all relapses up to EOS/cut-off and for confirmed relapses up to EOS/cut-off.
- Number (%) of relapses (out of total number of relapses) requiring hospitalization, treated with corticosteroids and descriptive statistics for continuous data for relapse duration (days); for all relapses up to EOS as well as for confirmed relapses up to EOS.

Full details of all relapses will be presented in a listing.

5.3.2.2.3. Time to first (confirmed) relapse

The analysis of time from randomization in the core study to first confirmed relapse during the Combined Analysis Period (up to EOS/cut-off for subjects entering the extension study or up to core EOS for subjects not entering the extension study) will be performed on the FAS and EXTS using KM methods.

Time to first confirmed relapse will be summarized on the FAS in a table including, the number of subjects with event / censored, KM estimates and corresponding CI (anticipated time points of 24-week intervals: 24, 48, 72, 96, 120, 144, 168, 192, 216, 240, 264 and 288 weeks), and median (as well as 25th and 75th percentiles) of the survival function together with CIs. A graphical display presenting a KM plot going upward is presented, including CIs at specific time points. Intervals will be displayed 24 weeks up to the last time point.

Censoring rules are defined in Section 5.3.1.1.2. The analysis will be repeated for time to first relapse including all relapses.

Time to first relapse and time to first confirmed relapse data will be listed using the FAS.

5.3.2.3. Analysis of MRI-related variables

5.3.2.3.1. T1 Gd+ lesions

The total number of Gd+ T1 lesions per visit will be summarized descriptively as continuous data and in categories (anticipated categories: 0, 1, 2, 3, 4, 5, 6-10, 10+), for the Combined Analysis Period on the EXTS.

Descriptive statistics on absence of Gd+ T1 lesions (frequency and percentages of subjects with lesions absent, present) will be presented by visit, and cumulative for absence of Gd+ T1 lesions from Core baseline up to extension EOT will be tabulated. This analysis will be done for combined period using EXTS.

The total number of Gd+ T1 lesions will be analyzed by visit for the Combined Analysis Period on the EXTS using a negative binomial regression model: the response variable is the number of lesions at the respective visit, with core study treatment as a factor and no offset. Mean model-based estimates and corresponding 95% CIs will be presented. The corresponding plots will also be presented.

Total volume of T1 hypointense lesions and the change from core baseline per visit is summarized descriptively based on observed data, for combine analysis period using the EXTS. In addition, total volume of T1 hypointense lesions and the change from extension baseline per visit is summarized descriptively for extension period using EXTS. The total volume of T1 hypointense lesion data will be listed using FAS.

Descriptive statistics of the proportions of Gd+ T1 lesions at core baseline evolving to persistent black holes will be presented by visit in the subset of subjects with Gd+ T1 lesions present at baseline using the EXTS for combined period. Same analysis in relative to extension baseline (i.e. Core study EOT) will be repeated using EXTS during extension period. A listing will be prepared using the FAS.

Gd+ T1 lesions data will be listed on the FAS.

5.3.2.3.2. New or enlarging T2 lesions

The total number of new or enlarging T2 lesions per visit will be summarized descriptively as continuous and in categories (anticipated categories: 0, 1, 2, 3, 4, 5, 6-10, 11+), for the Combined Analysis Period on the EXTS.

The cumulative number of new or enlarging T2 lesions from core baseline up to extension EOS (Combined Analysis Period) (i.e. from baseline up to extension EOS) will be analyzed on the EXTS using a negative binomial regression model with core study treatment as a factor and the log of time up to last MRI (in years) considered for analysis as an offset variable. Mean model-based estimates and corresponding 95% CIs will be presented. The same model is applied for extension period on the EXTS.

Descriptive summary statistics for the cumulative number of new or enlarging T2 lesions from core baseline up to extension EOS on the EXTS will be presented by treatment group for continuous data and frequency per categories (anticipated: 0, 1–5, 6–10, 11-20, 20+), total counts and total cumulative observation time (time up to the last MRI scan in years) summed for all subjects, raw yearly rate (total count / total cumulative observation time). Descriptive summary statistics for the cumulative number of new or enlarging T2 lesions from extension baseline up to extension EOS on the EXTS will be presented in the same way.

Descriptive statistics on absence of new or enlarging T2 lesions by visit (frequency and percentages of subjects with lesions absent, present) will be presented by visit, and cumulative for absence of new or enlarging T2 lesions from Core baseline up to extension EOS will be tabulated. This analysis will be done for combined period using EXTS.

The total number of new or enlarging T2 lesions will be analyzed by visit for the Combined Analysis Period on the EXTS, using the negative binomial model, as described in Section 5.3.2.3.1, for the total number Gd+ T1 lesions per visit. The corresponding plots will also be presented.

Total volume of T2 lesions and change from baseline per visit is summarized descriptively based on observed data, for combine analysis period using the EXTS. Same analysis will be repeated using EXTS relative to Extension baseline during Extension period. The total volume of T2 lesion data will be listed using FAS.

T2 lesion data will be listed on the FAS.

5.3.2.3.3. Combined unique active lesions (CUAL)

The total number of CUAL lesions at Week 60 and at Week 108 of the core study, and Week 48, Week 96, Week 144, Week 192, Week 240, Week 288 and EOT of the extension study, will be analyzed by visit for the Combined Analysis Period on the FAS and EXTS, using the negative binomial model: the response variable is the number of CUAL at respective visit, with study treatment at core baseline as a factor and no offset. Model based estimates and the corresponding 95% CI will be tabulated. The corresponding plots will also be presented.

The total number of CUAL per visit will be summarized descriptively as continuous and in categories (anticipated categories: 0, 1–5, 6–10, 11-15, 16-20, 21-25, 26+), for the Combined Analysis Period on the FAS and EXTS.

The cumulative number of CUAL will be analyzed using a negative binomial regression model, similar as described in Section 5.3.2.3.2 for the cumulative number of new or enlarging T2 lesions, but using log of the total years from core baseline to last MRI scan as offset variable. CUAL will be analyzed from:

- Core baseline up to extension EOS (Combined Analysis Period) using EXTS;
- Extension baseline up to extension EOS (Extension Analysis Period) on the EXTS;

Descriptive summary statistics of the number of CUALs from core baseline up to extension EOS (Combined Analysis Period) using EXTS will be presented for continuous data and in categories (0, 1–2, 3–5, 6-10, 11-15, 16-20, 21-25, 26-30, 31-35, 36-40, 41+). The total number of CUALs as well as the total cumulative time up to the last MRI scan (summed for all subjects) will also be displayed. From the total number of CUALs and the total cumulative time up to the last MRI scan the raw number of CUALs per year will be calculated and summarized. Descriptive summary statistics for the number of CUALs from extension baseline up to extension EOS (Extension Analysis Period) on the EXTS will be presented in the same way.

In addition, the cumulative CUAL up to each visit during combined analysis period will be analyzed on FAS and EXTS using a negative binomial regression model, similar as described in Section 5.3.2.3.2 for the cumulative number of new or enlarging T2 lesions, but using log of the total years from core baseline to last MRI scan as offset variable. Model based estimates and the corresponding 95% CI will be tabulated. The corresponding plots will also be presented.

A listing of CUAL data will be presented using FAS.

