1.2. Study Design and treatment period

Study AC-058B303 (the "extension study") is a prospective, multi-center, open-label, non-comparative, long-term extension of the Phase 3 confirmatory AC-058B301 (the "core study"). Details of the AC 058B301 study can be found in the study Protocol Final Version 7, dated 5 December 2018.

Subjects who have completed the 108-week treatment period in the core study will be enrolled as one group treated with ponesimod 20 mg once daily in the extension study, independent of previous treatment allocation.

The extension study consists of a pre-treatment period, a treatment period, and a safety follow-up.

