1.2.1. Core study follow up period and transition into the extension study

Eligible subjects may enter the extension study following the safety follow-up (FU) period of the core study. For subjects transitioning into the extension study, the core study safety FU period concludes with a safety Follow-up Visit 1 (FU1) or with an abbreviated Follow-up Visit 2 (FU2) at 14-22 and 23-37 days, respectively, after the last dose of the study drug in the core study (End of-Treatment; EOT). The abbreviated FU2 visit will take place only if the compliance with teriflunomide elimination procedure was deemed not sufficient by the investigator at FU1 visit but transition to the extension study is still planned. The core study FU period ends when all assessments of FU1 or FU2 (whichever applies) have been completed. At FU1 or FU2 (whichever applies) the subject's compliance with teriflunomide elimination procedure needs to be assessed as sufficient by the investigator in order to confirm eligibility for the extension study.

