5.3.1.2.2. New or enlarging T2 lesions

The following variables will be evaluated at each visit:

- Total number of new or enlarging T2 lesions (relative to previous visit), derived as: Number of new or enlarging T2 lesions without gadolinium-enhancement (T2new_R) + new or enlarging T2 lesions with gadolinium-enhancement (T2newGd R);
- Total number of new or enlarging T2 lesions (relative to previous visit) categorized (0, 1–5, 6–10, 11+);
- Cumulative new or enlarging T2 lesions from core baseline up to each visit up to extension EOS. Cumulative new or enlarging T2 lesions will not be derived if any post-baseline record is missing with a reason of "Dependent evaluation missing: Reference required for evaluation is not available (missing or rejected)" in the SDTM variable MO.MOREASND.

Where "new" refers to last prior available scheduled visit (note: planned pregnancy visits are considered scheduled MRIs for analysis), and specifically for evaluations at extension study Visit 7, results are compared to Visit 14 EOT from the core study.

In addition, the follow cumulative variables are derived:

The cumulative number of new or enlarging T2 lesions from core baseline to extension EOS is derived as the sum of number of the sum of total number of new or enlarging T2 lesions (as derived above) at all post-baseline MRI at all post-core baseline MRI scans up to the extension EOT MRI visit. This includes premature EOT scans if available, and unscheduled scans only if it is the last available scan for the subject.

The time up to the last MRI (years) included in the above is derived as = Date of last MRI considered in derivation - core randomization date + 1 divided by 365.25 days.

Similarly, the cumulative number of new or enlarging T2 lesions from extension baseline to extension EOS is derived as described above, together with the time, where time is relative to enrollment in the extension study.

If the baseline MRI is missing, new or enlarging T2 lesions as compared to baseline cannot be assessed and consequently the endpoint is considered missing. The baseline MRI is considered missing if presence of T1 Gd+ lesions at baseline is missing. The following analyses will be conducted as well:

- **Absence of new or enlarging T2 lesions at each visit:** 'New or enlarging T2 lesions' are considered 'absent', if the number of New or enlarging T2 lesions at each visit is zero. If > 0 they are considered 'present'. This applies to nominal visit collected in the CRF.

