5.3.1.2.3. Combined unique active lesions (CUAL) and cumulative CUAL

The number of combined unique active lesions (CUAL) at each scan visit is defined as the sum of new T1 Gd+ lesions (T1GdNew R) and new or enlarging T2 lesions without gadoliniumenhancement (T2New R) at each scan visit. Categorization of CUAL at each visit is (0, 1-5, 6-10, 11-15, 16-20, 21-25, 26+).

The cumulative number of CUAL from core baseline to extension EOS is defined as the sum of new T1 Gd+ lesions (T1GdNew R) and new or enlarging T2 lesions without gadoliniumenhancement (T2New R) (i.e., without double-counting the lesions) at all post-baseline MRI visits up to the extension EOS. This includes premature EOT scans, if available, and unscheduled scans only if it is the last available scan for the subject. Categorization of cumulative CUAL at each visit is (0, 1–5, 6–10, 11-15, 16-20, 21-25, 26-30, 31-35, 36-40, 41+).

The cumulative number of CUAL from extension baseline to extension EOS is also derived as described above.

The time up to the last MRI (years) included in the above is derived as = Date of last MRI considered in derivation – core randomization date / extension enrollment date + 1 divided by 365.25 days.

Note that CUAL will be calculated at each visit only if baseline Gd+ T1 lesions is available and "New or enlarging T2 lesions" is not missing at that visit. Otherwise the CUAL is set to be missing.

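### Section 5.3.2.3.3 puts a core-baseline offset on the extension-period CUAL model, contradicting the period-specific time in 5.3.1.2.3; applied as written, it would understate the extension lesion rate

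*SAP*

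**What the plan says.** Section 5.3.2.3.3 specifies a negative binomial model for cumulative CUAL. It takes the T2 lesion model as its pattern, "but using log of the total years from core baseline to last MRI scan as offset variable. CUAL will be analyzed from" two starting points. The first is core baseline (Combined Analysis Period). The second is "Extension baseline up to extension EOS (Extension Analysis Period) on the EXTS". No other offset is given for the second model. A further analysis in the same section, in which "the cumulative CUAL up to each visit during combined analysis period will be analyzed on FAS and EXTS", repeats the same offset wording.

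The endpoint definition in section 5.3.1.2.3 differs. It derives the time to last MRI as the date of the last MRI considered in the derivation minus "core randomization date / extension enrollment date + 1 divided by 365.25 days", which gives one origin per period.

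The T2 model cited as the pattern is also period-specific. Its offset in section 5.3.2.3.2 is "the log of time up to last MRI (in years) considered for analysis as an offset variable", and section 5.3.1.2.2 defines the extension version of that time as one "where time is relative to enrollment in the extension study".

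The SAP is also inconsistent on whether the analysis exists. Table 4 marks CUAL as not analyzed in the Extension Analysis Period. Table 6 marks both CUAL by visit and cumulative CUAL as analyzed there on the EXTS.

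**The concern.** In a log-link model with offset log(t), the fitted quantity is lesions per unit of t. Count and time must therefore cover the same interval. In the extension model as worded, the count covers the extension only, while the time also contains the 108-week core study and the gap between the studies. The estimated annual rate and both of its confidence limits are pulled down.

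The affected output is a model-based annual lesion rate on ponesimod during the extension. It bears directly on the objective of describing long-term disease control. The same section also asks for a raw number of CUALs per year for the extension. If that raw figure uses the time defined in 5.3.1.2.3, the raw and modelled rates for the same subjects would disagree, and a reader of the report would have no explanation for the difference.

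**Working it through.** The SAP states no CUAL rate, so there is no figure of its own to reproduce. The check is of the denominator.

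**Inputs**
- Core time: 108 weeks × 7 = 756 days. Section 1.2 enrols "Subjects who have completed the 108-week treatment period in the core study".
- Gap from last core dose to first extension dose: 14 to 45 days. The core follow-up visits fall "at 14-22 and 23-37 days, respectively, after the last dose of the study drug in the core study" (section 1.2.1), so 14 to 37 days. Table 12, footnote 2 allows up to 1 day more to consent and up to 7 days from consent to first dose: 37 + 1 + 7 = 45.
- Extension time to last MRI: 7 × week + 1 days. This matches the Table 7 target days for the MRI weeks: 337, 673, 1009, 1345, 1681 and 2017 for Weeks 48, 96, 144, 192, 240 and 288.

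**Formula**

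Understatement = 1 − T_ext / (756 + gap + T_ext)

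**Per-subject results, by week of last MRI**

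| Last MRI | T_ext (days) | Gap 14 days | Gap 45 days |
|---|---|---|---|
| Week 48 | 337 | 1 − 337/1107 = 69.6% | 1 − 337/1138 = 70.4% |
| Week 96 | 673 | 1 − 673/1443 = 53.4% | 1 − 673/1474 = 54.3% |
| Week 144 | 1009 | 1 − 1009/1779 = 43.3% | 1 − 1009/1810 = 44.3% |
| Week 192 | 1345 | 1 − 1345/2115 = 36.4% | 1 − 1345/2146 = 37.3% |
| Week 240 | 1681 | 1 − 1681/2451 = 31.4% | 1 − 1681/2482 = 32.3% |
| Week 288 (Ukraine only) | 2017 | 1 − 2017/2787 = 27.6% | 1 − 2017/2818 = 28.4% |

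A premature end-of-treatment MRI at Day 246, the start of the Week 48 MRI window in section 5.1.10, gives 1 − 246/1016 = 75.8% to 1 − 246/1047 = 76.5%.

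The table counts extension time from first dose. Section 5.3.1.2.3 counts from enrollment, at most 7 days earlier. At Week 48 with the longest gap, that changes 70.4% to 1 − 344/1138 = 69.8%, so the choice does not matter here.

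**Group-level illustration**

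The model reports group rates, not per-subject ratios. To see where a pooled value might fall, negative binomial models were fitted to simulated data under both offsets. The settings were 877 subjects, a gap of 20 days, dispersion 1.5 and a true rate of 1 lesion per year. Only the 877 comes from the SAP; the rest, including the follow-up mixes, is assumed.

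| Assumed mix of last MRI (Weeks 48 / 96 / 144 / 192 / 240 / 288) | Understatement of pooled rate |
|---|---|
| 5 / 5 / 5 / 5 / 75 / 5% | 35% |
| 10 / 10 / 10 / 10 / 55 / 5% | 39% |
| 20 / 20 / 20 / 20 / 20 / 0% | 46% |

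With the time defined in 5.3.1.2.3, numerator and denominator use the same period and this error disappears.

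**The case against.** The strongest reply is that the right variable is already in the SAP. Section 5.3.1.2.3 defines the time with an extension-enrollment origin, and 5.3.2.3.3 calls its model similar to a T2 model that uses period-specific time. A programmer who works from the endpoint definition would get the extension rate right. This stands as a limit on the claim: the error is conditional. It does not remove the defect. The analysis section departs from the T2 pattern explicitly and names core baseline as the origin, so two sections give two different denominators for one planned model.

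A second reply is that little hangs on this output. Section 2 states that no hypotheses are pre-specified and that all analyses are exploratory. The main efficacy analysis is on the Combined Analysis Period, where the core origin is correct. Table 4 does not even list CUAL for the extension period. All of that stands and lowers the stakes. However, descriptive estimates are what this study delivers, and Table 6 and section 5.3.2.3.3 do plan this one.

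A reader might also infer that the per-visit cumulative analysis is wrong, with lesions up to an early core visit divided by a subject's entire follow-up. The documents do not support that. The analysis is on the combined period, so core baseline is the right origin, and 5.3.1.2.3 ends the time at the last MRI considered in the derivation. For a count up to a visit, this is naturally the last scan up to that visit. A clarifying phrase is all that is needed.

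**Conclusion.** Section 5.3.2.3.3 is wrong as written for the extension-period CUAL model and contradicts 5.3.1.2.3. If it is followed literally, the annual rate is understated per subject by about 28% (last MRI at Week 288) to about 70% (Week 48), and by about 76% for a premature scan at Day 246. These figures assume a full 108-week core period and a gap of 14 to 45 days.

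Two stronger conclusions are tempting and do not follow:

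- **That the reported extension rate will be up to 70% too low.** The per-subject range is not the bias of a group estimate; a 70% group bias would require every subject's last MRI to be at Week 48. The group bias is one value set by the follow-up mix, which the SAP does not give. The 35 to 46% above is illustrative only.
- **That the comparison between core treatment groups is distorted.** That would need different follow-up by core group, and nothing in the SAP shows this. With similar follow-up the contrast is little affected, and the absolute rates carry the error. Section 5.3.2.3.3 plans no CUAL rate ratio; it asks for model-based estimates with confidence intervals.

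**What to change.** Amend section 5.3.2.3.3 so that each model carries its own offset:

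- Extension-period model: log of the years from extension enrollment to the last MRI considered in the derivation, as in 5.3.1.2.3.
- Combined-period models: log of the years from core randomization to the last MRI considered in the derivation.
- Cumulative CUAL up to each visit, as a clarification only: the time ends at the last scan included up to that visit.

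Reconcile Table 4 with Table 6 on whether CUAL is analyzed in the Extension Analysis Period.

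The core end-of-treatment scan could be argued for as the extension origin, because section 5.3.1.2.2 compares Visit 7 lesions with that scan. That would be a change of definition and is not needed to remove the contradiction.

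The cost is one paragraph of SAP text, one table entry and a check of which time variable the program uses. No new data are needed.

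### SAP 5.3.2.3.3 starts the clock of the extension-period cumulative CUAL model at core baseline, contradicting 5.3.1.2.3, which starts it at extension enrollment

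*SAP*

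**What the plan says.** Section 5.3.2.3.3 models cumulative CUAL in the same way as cumulative T2 lesions, with one stated departure: "but using log of the total years from core baseline to last MRI scan as offset variable. CUAL will be analyzed from". Two analyses follow. The first runs from core baseline to extension EOS. The second is "Extension baseline up to extension EOS (Extension Analysis Period) on the EXTS". No other offset is given for the second.

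Section 5.3.1.2.3 defines the counts and the time variable. After the combined-period count it adds: "The cumulative number of CUAL from extension baseline to extension EOS is also derived as described above". It then computes time to the last MRI by subtracting "core randomization date / extension enrollment date + 1" and converting to years. The slash gives each period its own origin: core randomization for the combined period and extension enrollment for the extension period.

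The T2 lesion sections work the same way. In 5.3.1.2.2 the extension count comes with its own time, "where time is relative to enrollment in the extension study". Section 5.3.2.3.2 uses the log of time to the last MRI considered as offset and states: "The same model is applied for extension period on the EXTS".

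The tables disagree on whether CUAL is analysed in the extension period at all. Table 4 marks it N; Table 6 marks cumulative CUAL Y for that period.

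**The concern.** Read literally, the extension model has a numerator and a denominator from different periods. The numerator leaves out lesions found during the core study, while the denominator includes all of that study. Because 5.3.2.3.3 introduces its offset as a departure from the T2 model, a programmer working from the analysis section could reasonably take it as intended for both analyses.

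The extension would then look quieter by construction. Both analyses use the EXTS and would share one denominator, and the extension count cannot exceed the combined count. The raw extension rate on that denominator could therefore never exceed the combined rate, whatever the drug does. The model-based extension rate would also disagree with the raw extension CUALs per year if that summary uses the time from 5.3.1.2.3. In a non-comparative extension meant to describe disease control, absolute yearly rates are among the main products.

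**Working it through.** The SAP gives no numerical CUAL rate, so there is no figure of its own to reproduce. The check is how far the two denominators differ.

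**Inputs**

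- Core period: 108 weeks (1.2: "Subjects who have completed the 108-week treatment period in the core study"), 108 × 7 = 756 days, taken as the time from randomization to core EOT.
- Gap: the core follow-up visit falls up to 37 days after the last core dose (1.2.1) and the pre-treatment period lasts up to 7 days (1.2.2). The range used is 0 to 37 + 7 = 44 days.
- Last extension MRI: scheduled at Weeks 48, 96, 144, 192 and 240, and at Week 288 in Ukraine (5.3.1.2). Target days are from Table 7. The earliest premature EOT scan mapped to Week 48 is Day 246 (5.1.10).
- Extension Day 1 stands in for enrollment. The two differ by at most 7 days, which leaves the results within the ranges shown.

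**Formula.** For a last MRI on extension day d:

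rate as written ÷ rate on the extension clock = d / (756 + gap + d)

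understatement = (756 + gap) / (756 + gap + d)

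Example at Week 240: 756 / (756 + 1681) = 31.0% with no gap; 800 / (800 + 1681) = 32.2% with a 44-day gap.

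| Last extension MRI | d | Years, extension clock | Years, core clock | Rate too low by |
|---|---|---|---|---|
| Premature EOT scan | 246 | 0.67 | 2.74–2.86 | 75.4–76.5% |
| Week 48 | 337 | 0.92 | 2.99–3.11 | 69.2–70.4% |
| Week 96 | 673 | 1.84 | 3.91–4.03 | 52.9–54.3% |
| Week 144 | 1009 | 2.76 | 4.83–4.95 | 42.8–44.2% |
| Week 192 | 1345 | 3.68 | 5.75–5.87 | 36.0–37.3% |
| Week 240 | 1681 | 4.60 | 6.67–6.79 | 31.0–32.2% |
| Week 288 (Ukraine) | 2017 | 5.52 | 7.59–7.71 | 27.3–28.4% |

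These are per-subject figures.

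**Group level.** A simulation fitted the negative binomial model with each offset. It used 877 subjects and a 20-day gap. The rates of 1.3 and 1.0 lesions per year in the two core groups, a dispersion of 2, and the mix of last-scan times (8% at each of Weeks 48, 96, 144 and 192; 68% at Week 240) are assumptions. Averages over 40 runs:

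| Offset | Group 1 rate | Group 2 rate | Rate ratio |
|---|---|---|---|
| From extension enrollment | 1.30 | 0.99 | 0.77 |
| From core baseline | 0.82 | 0.62 | 0.76 |

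The absolute rates fall by 1 − 0.82/1.30 = 37% and 1 − 0.62/0.99 = 37%. The ratio barely moves because both groups' times are inflated by about the same amount.

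**The case against.** The strongest reply is that the SAP does not consistently prescribe the wrong denominator. The right one is already derived in 5.3.1.2.3, the T2 sections use an extension clock, and 5.3.2.2.2 uses period-specific observation time for relapses. The same offset wording recurs at the end of 5.3.2.3.3 for a combined-period model, where a core-baseline start fits, so it may simply have been carried over. This stands: the point is a contradiction to resolve, and bias arises only if 5.3.2.3.3 is followed against 5.3.1.2.3.

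A reader might infer that the reported extension rate is understated by 31% to 70%. The documents do not support that. The figures are conditional, they are per subject, and they are not bounds, as the Day 246 and Week 288 rows show. The SAP gives no distribution of last-scan times from which a group figure could be derived.

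A reader might also infer that no counted lesion can arise between the core study and enrollment. That is wrong. In 5.3.1.2.2 the first scheduled extension scan is compared with the core EOT scan, and 5.3.1.2.4 equates extension baseline with core EOT for brain volume. With a clock from that scan, the understatement is 756 / (756 + gap + d). For gaps of 14 to 44 days this is 68.3% to 66.5% at Week 48 and 30.8% to 30.5% at Week 240, so the conclusion is little changed.

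Finally, importance is limited. Section 2 calls all analyses exploratory, and 5.1.5.1 and 6.2.1 place the main efficacy focus on the combined period. Extension T2 rates and raw CUAL counts are also reported, so a discrepancy might be noticed. This bears on weight, not on whether the text needs correcting.

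**Conclusion.** The contradiction is real. Section 5.3.2.3.3 gives one core-baseline offset to both cumulative CUAL models, while 5.3.1.2.3 gives the extension period its own clock. If 5.3.2.3.3 is programmed literally, the model-based extension CUAL rates and their confidence limits are too low. The per-subject shortfall is about 31–32% for a last MRI at Week 240, 53–54% at Week 96 and 69–70% at Week 48. These figures assume a 108-week core period, a gap of 0 to 44 days and scans on target days. The group-level figure of about 37% rests wholly on the assumed scan mix and should be read as an illustration.

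The comparison between core treatment groups is nearly unaffected, no hypothesis test is involved, and a core-baseline start suits the combined-period models. Calling this the principal lesion result would go too far: it is a secondary exploratory estimate whose place in the extension period is itself unclear between Tables 4 and 6. It still merits correction, because the possible error is large, always in one direction, and easy to remove.

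**What to change.** In 5.3.2.3.3:

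- State that the offset for the Extension Analysis Period model is the log of years from extension enrollment to the last MRI considered, as derived in 5.3.1.2.3. Name enrollment explicitly: extension baseline would be ambiguous, since the reference MRI is the core EOT scan.
- Limit the core-baseline offset to the Combined Analysis Period models.
- State that the raw extension CUALs per year use the same extension-enrollment time.

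Separately, reconcile Table 4 (N) with Table 6 (Y) on CUAL in the extension period.

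The cost is a few lines of wording. The time variable is already derived, and no new data or model is needed.
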